3.3 Secondary Outcomes

The secondary endpoints for each aim are shown in **Table 3**.

Table 3. Secondary endpoints for each study aim of this multisite, randomized controlled pilot and feasibility trial

Aim 1: Test multisite fidelity of training/implementation of 6-week group MBI, CBT, and HealthEd to adolescent girls and boys at-risk for T2D with depression symptoms		
Objective	Endpoint	Metric; Analysis
Training Fidelity (Secondary)	6-months	Facilitators score ≥80% on post-training knowledge/competency tests of MBI, CBT, and HealthEd
Training Fidelity (Secondary)	6-months	Facilitators score ≥8 on adherence and competence ratings of MBI, CBT, and HealthEd mock group sessions (1=poor to 10=exceptional)
Aim 2: Evaluate multisite feasibility/acceptability of recruitment, retention, and adherence for a protocol involving randomization to 6-week group MBI, CBT, or HealthEd with 6-week and 1-year follow-up		
Objective	Endpoint	Metric; Analysis
Recruitment Feasibility (Secondary)	12-months	Attainment of target N=120 within a 12-month period; CONSORT flow/number of months to reach recruitment goal
Intervention Feasibility (Secondary)	6-weeks	≥80% adolescents attend 5:6 (80%) group MBI/CBT/HealthEd sessions
Intervention Acceptability (Secondary)	6-weeks	≥80% adolescent liking/credibility ratings ≥4 (1=not at all to 5=extremely)
Intervention Acceptability (Secondary)	6-weeks	Themes indicative of acceptability of interventions, as derived from grounded theory/qualitative analysis of adolescent focus-groups at post-intervention
Retention Feasibility (Secondary)	12-months	≥80% at post-treatment follow-up and ≥70% at 1-year follow-up
Assessment Feasibility (Secondary)	18-months	≥95% accuracy on standardized protocol checklists for all assessments

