Administration: All three interventions will be delivered by a clinical or counseling psychologist. Programs will be co-facilitated by a graduate student in clinical or counseling psychology, social work, prevention science, or related field, or a research associate with a master's degree in clinical or counseling psychology, social work, prevention science, or related field. Psychologists and co-facilitators will participate in MBI, CBT, and HealthEd training. Sessions will be audio-recorded and reviewed weekly by [name] (MBI) and [name] (CBT, HealthEd) for adherence and competence. Feedback will be provided in weekly supervision. Facilitators with drift or deficiencies will be re-trained via "booster sessions" as needed. To minimize facilitator effects, psychologist facilitators at each site will facilitate all three programs.

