5. STUDY INTERVENTIONS

5.1 Interventions

Overview: In this three-arm multisite, randomized controlled pilot and feasibility trial, mindfulness-based intervention (MBI), cognitive-behavioral therapy (CBT), and health education (HealthEd) group programs are matched for time, attention, and facilitator training. All

interventions will be delivered for six weekly 1-hour group-based sessions. Group sessions will either take place via secure videoconferencing or in a conference room at each respective site. All interventions will be delivered by a clinical or counseling psychologist. Programs will be co-facilitated by a graduate student in clinical or counseling psychology, social work, prevention science, or related field, or a research associate with a master's degree in clinical or counseling psychology, social work, prevention science, or related field. To minimize facilitator effects, the lead psychologist facilitators at each site will facilitate all three programs. All facilitators and co-facilitators will receive training and weekly supervision as described below. Interventionists cannot be blinded to intervention assignment due to the nature of the intervention.

Intervention Training: All three interventions are manualized. Utilization of manuals for each of the three conditions supports fidelity, which will be closely monitored. Prior to delivery of the interventions as part of the multisite, pilot clinical trial, lead psychologist facilitators and co-facilitators will participate in MBI, CBT, and HealthEd training. The training will be 5-days (~3 days for MBI, ~1 day for CBT, ~1 day for HealthEd). We prefer to conduct the training in-person, but if circumstances (e.g., due to COVID-19) are more conducive to remote training, we will deliver some or all portions of the training remotely via videoconferencing. All trainings will video-recorded for future reference/training by the study team.

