Training will include presentations of theoretical/empirical background, review of manuals, modeling of session elements, and role-play in mock-groups. [name] (Co-I), a psychologist completing BREATHE master training certification with [name] (Consultant; BREATHE developer), will lead training in BREATHE, the MBI program. [name] has expertise delivering BREATHE with high fidelity/competence to at-risk teenagers. [name] (Co-I), a psychologist trained in the Blues Program by [name] (Consultant) and his team of Blues Program developers ([name], [name]) and in HealthEd by [name] (PI), will facilitate training in the CBT Blues Program and the didactic control program, HealthEd. [name] has demonstrated high fidelity/competence in CBT and HealthEd, as rated by the Blues Program development team and [name].

To assess training fidelity: a) MBI, CBT, and HealthEd training sessions will be video-recorded and rated by [name], [name], and [name], respectively, on training fidelity forms; b) Facilitators will complete post-training surveys assessing quantitative knowledge of MBI, CBT, and HealthEd, following the didactic portion of the training; and c) Facilitators' adherence and competence in conducting mock intervention sessions will be evaluated by experts (Drs. [name], [name]/[name]/[name], and [name]) on standardized ratings scales to establish training fidelity prior to delivery to participants. Facilitators also will provide qualitative feedback on any recommended modifications to training procedures that they perceive would improve the training process, for use in a future NIH/NCCIH UG3/UH3 grant application/multisite efficacy trial. For descriptive purposes, facilitators will complete surveys of quantitative intervention knowledge prior to the didactic training, as well as feedback following the mock session training portion.

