8.6 Data Analyses

8.6.1 Primary Analyses

In Aim 1, descriptive analyses will be conducted to: (i) describe post-training knowledge/competency of MBI, CBT, and HealthEd to determine if facilitators score $\geq 80\%$; (ii) describe adherence and competence ratings of mock group sessions of MBI, CBT, and HealthEd to determine if ratings ≥ 8 (1-10 scale with 10 being the most positive valence); and (iii) describe adherence and competence ratings of pilot group sessions of MBI, CBT, and HealthEd by blinded, expert reviewers to determine if ratings ≥ 8 . Chi-square analyses will be used to explore whether the percentages meeting these criteria vary across conditions (MBI vs. CBT vs. HealthEd) and site. In Aim 2, study flow will be described according to CONSORT guidelines for the reporting of clinical trials.^{176,177} Descriptive analyses will be generated to determine: (i) the percentage of adolescents who enroll after being determined to be eligible, (ii) number of months to reach recruitment goal, (iii) percentage of adolescents who attended 5 of 6 ($\geq 80\%$ sessions), (iv) percentage of adolescents whose likability/credibility ratings were ≥ 4 (1-5 scale, with 5 being the most positive valence), (v) percentage of adolescents who complete post-treatment and 1-year follow-up assessments, and (vi) percentage compliance with standardized operating procedure checklists for all assessments. Analyses of variance (ANOVA) and chi-square will be used to describe any potential differences across the 4 sites and the 3 intervention arms. A Tukey adjustment will be used to control for multiple comparisons. For the primary analyses in Aims 1 and 2, we do not plan to adjust for covariates as our interest is in estimating measures of success independent of participant characteristics.

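### Training pass rates are compared across the three programs and across sites by chi-square, although the same facilitators are scored in every program; the comparison should be blocked on facilitator.

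*Combined protocol and SAP*

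**What the plan says.** Section 8.6.1 lists three Aim 1 criteria to be described: (i) post-training knowledge of at least 80%, (ii) mock-session ratings of at least 8, and (iii) ratings of at least 8 for sessions delivered in the trial. It then adds: "Chi-square analyses will be used to explore whether the percentages meeting these criteria vary across conditions (MBI vs. CBT vs. HealthEd) and site". No paired, blocked or clustered version of the test is named.

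On who is scored, Section 3.7 says "Psychologists and co-facilitators will participate in MBI, CBT, and HealthEd training", and Section 5.1 repeats that "lead psychologist facilitators and co-facilitators will participate in MBI, CBT, and HealthEd training". Section 5.1 continues: "Facilitators will complete post-training surveys assessing quantitative knowledge of MBI, CBT, and HealthEd", and "Facilitators' adherence and competence in conducting mock intervention sessions will be evaluated by experts". The secondary endpoint in Section 3.3 is worded "Facilitators score ≥80% on post-training knowledge/competency tests of MBI, CBT, and HealthEd".

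On who delivers the programs, Section 3.7 says "To minimize facilitator effects, psychologist facilitators at each site will facilitate all three programs".

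**The concern.** Each trained facilitator supplies an MBI, a CBT and a HealthEd result. The three columns of the condition table are therefore the same people measured three times. A Pearson chi-square treats them as three separate groups. Fisher's exact test makes the same assumption, so switching to it would not help.

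Two things follow if able trainees tend to do well in every program:

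- **Condition.** Differences between people remain in the error term although they cancel within a person. A program that is harder to learn is more likely to be missed.
- **Site.** If the three results per person are put into one site table, each person counts three times, and one weak trainee can look like a site difference.

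Using the same leads in all programs creates a blocked design. The planned test gives up the benefit of that blocking.

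**Working it through.** **1. The plan's own figure.** Section 8.2 gives no facilitator count, alpha or power for these tests. The nearest figure is the 24% width of the 95% CI for session fidelity (true proportion 0.85, ICC 0.06, 4 clusters of 16 sessions, CV 0.01).

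- Design effect = 1 + ((1 + 0.01²)×16 − 1)×0.06 = 1.90
- Effective n = 64/1.90 = 33.7
- Width = 2×1.96×√(0.85×0.15/33.7) = 24.1%

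The figure is reproduced. The plan therefore allows for clustering by facilitator in its precision estimate but not in the test.

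**2. Large-sample size of the chi-square.** Let ρ be the common correlation between a person's three pass/fail results. Under no true difference, the condition statistic behaves as (1 − ρ)χ² on 2 df and the pooled site statistic as (1 + 2ρ)χ² on 3 df. The nominal 5% test then rejects with these probabilities:

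| ρ | Condition: P(χ²₂ > 5.991/(1−ρ)) | Pooled site: P(χ²₃ > 7.815/(1+2ρ)) |
|---|---|---|
| 0.06 | 4.1% | 7.3% |
| 0.30 | 1.4% | 18% |
| 0.50 | 0.25% | 27% |

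**3. Small samples.** These runs assume 8 facilitators (a lead and a co-facilitator at each of 4 sites) or 12, pass rates of 50–80% and ρ of 0.25–0.45. None of these values is in the documents. Simulated false rejection is about 1–3% for condition and about 12–29% for pooled site. The lowest site cell is 11% (8 facilitators, pass rate 80%, ρ = 0.25); the top comes from pass rate 50% with ρ = 0.45. At ρ = 0.06 the same runs give about 4–5% for condition and 5–8% for pooled site. Testing site within one program shows no inflation from ρ.

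**4. Worked tables.** Cochran's Q = 2(3ΣC² − N²)/(3N − ΣR²), where C are program totals of passes, R are facilitator totals and N is the overall total.

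- *Two of 8 fail everything and four more fail MBI only.* Passes are 2, 6, 6. Pearson X² = 5.49, p = 0.064. Q = 2(3×76 − 14²)/(3×14 − 34) = 64/8 = 8, p = 0.018. Exact within-facilitator p = 3/81 = 0.037.
- *Four of 8 fail MBI only.* Passes are 4, 8, 8. Pearson p = 0.008. Q is again 8: p = 0.018, exact 0.037.
- *Twelve facilitators with passes 6, 10, 10.* Pearson p = 0.109 whoever failed. If the same people fail across programs, Q gives p = 0.018. If different people fail, it gives p = 0.20.
- *Site: one of 8 fails all three.* Pooled table (3 of 6 results failed at one site, 0 of 6 at the others): p = 0.016. One value per facilitator (1 of 2 against 0 of 2): p = 0.33.

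**5. What a replacement gains.** With 8 facilitators and true pass rates of 50/90/90%, power is 49–50% for the planned chi-square, 52–58% for large-sample Q and 32–35% for exact Q. Large-sample Q stays at or below 5% under the null. On the underlying scores, with one program 1 SD lower and correlation 0.3, 0.5 or 0.7, power is 45%, 43% and 41% when the pairing is ignored and 60%, 75% and 93% when it is used. The score figures compare two score analyses. They do not measure what the chi-square itself loses.

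**The case against.** The case against has real weight.

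- **Little rests on these p-values.** Section 8.6.1 uses the tests to explore, sets no alpha, and judges training by fixed thresholds. Section 1.2 bases the revision of training on expert and trainee feedback. A reader might infer that training will be revised on the chi-square result, or that the ≥80% and ≥8 endpoints are compromised. The documents support neither.
- **The direction of error.** A reader might infer that the MBI/CBT/HealthEd p-values are wrong in both directions. Under positive correlation that test errs towards conservatism. A single table can go the other way, as the second worked table shows, but this is not its average behaviour. Part of the 0.008 against 0.037 gap in that table also comes from small expected counts: Fisher's test on the same unpaired table gives 0.020.
- **Pooling is not stated.** The site inflation arises only if the three results per person are combined. The plan is silent on this.
- **The inputs are assumed.** At the only ICC in the plan, 0.06, both distortions are small. That value is for trial sessions, however, not for one person's test scores. Section 5.1 also does not say that everyone leads a rated mock session in every program.
- **An exact Cochran's Q alone would be worse than the planned test with about 8 people.** This stands and shapes the fix.

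Nothing elsewhere repairs the point. The mixed models in Section 8.6.2 cover depression, insulin resistance, stress-related behavior and stress physiology, not facilitator scores.

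**Conclusion.** The concern holds in a limited form. The documents establish that the same facilitators are trained in all three programs and take a knowledge test on each, and that the named test ignores this. The direction and size of the error depend on a positive within-facilitator correlation and on the number of facilitators, neither of which is given. With 8–12 facilitators and correlation of about 0.25–0.45, the condition test rejects falsely about 1–3% of the time, so it loses power. A pooled site test, if that is what is done, rejects falsely about 12–29% of the time. At a correlation of 0.06 neither matters much. What is at stake is any statement that one program is harder to train, or that one site trained less well. The threshold endpoints are untouched.

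**What to change.** In Section 8.6.1:

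- For (i) and (ii), make the main condition comparison a facilitator-blocked (repeated-measures or paired) analysis of the scores. Give Cochran's Q for the pass rates beside it, and do not rely on the exact Q alone.
- Compare sites with one value per facilitator, such as the mean over the three programs, or one program at a time.
- For (iii), keep facilitator/site as a block when arms are compared, because "the lead psychologist facilitators at each site will facilitate all three programs".
- Report counts by facilitator and program, and label the p-values descriptive.

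The cost is a few sentences of wording and a different test on data already planned. The limitation is that there are very few facilitators, so any test will be imprecise. Reporting the counts without p-values would also remove the error.

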8.6.2 Secondary Analyses

One goal of the secondary analyses is to assess for a signal of a clinically significant effect of the interventions on depression and insulin sensitivity, which would be important outcomes in a larger efficacy trial. For these analyses, we will follow the approach of Cocks and Torgesen,¹⁷⁸ in which one-sided 80% CI's are calculated for the treatment effect. If the appropriately powered pilot study does not show evidence of an effect, this does not necessarily preclude the main trial going forward. Careful consideration for the possible reasons for the lack of effect and regarding how the intervention can be strengthened are needed. However, powering a pilot study in this way ensures that it provides as much information as possible. Given our final sample size after accounting for attrition, the pilot study is powered to detect a standardized effect size of 0.3, which is considered a small to medium effect size.

Another purpose of secondary analyses is to supplement the mixed-methods analyses in Aim 3 used to refine study procedures and interventions in preparation for a future efficacy trial by understanding predictors associated with study outcomes, as well as mediators and moderators of intervention effects. This study is not designed as an efficacy study, and we will not necessarily have sufficient statistical power for the secondary analyses. However, results of these analyses may help inform changes to the interventions. We will examine predictors of participant attrition, attendance, and likability/credibility ratings. We will use multilevel mixed-effects models to examine change over time in measures of depression, insulin resistance, stress-related behavior, and stress physiology. These models will allow us to account for and estimate the correlation within study site and intervention cohort, as well as the correlation between repeated measures within a participant. ICC will be estimated using the method of Donner¹⁷⁹ for continuous variables and Ridout¹⁸⁰ for binary variables. The models will contain terms for group, time, and a group by time interaction. We will adjust for the baseline value of the outcome, and will also consider adjustment for baseline age, sex, race/ethnicity, particularly if these variables are not balanced across study groups. Models will be adjusted for baseline adiposity and change in adiposity to examine whether decreases in depressive symptoms improves insulin sensitivity independent of adiposity. If we find significant between-group differences in the insulin resistance, stress-related behavior, and stress physiology outcomes, we will test whether those effects are moderated by baseline depressive symptom severity (CES-D score) by including an interaction term in the model. We will also examine participant characteristics associated with these outcomes in order to better understand factors that moderate the response to intervention. Mediation analyses, using the product-of-coefficients method and bootstrapped standard errors, will be used to explore whether improvements in insulin sensitivity (if present) are mediated by changes in stress-related behaviors and stress physiology. Quantitative measures of group cohesion, therapeutic alliance, and perceived credibility/expectancy, summarized by intervention arm, will inform modifications to facilitator training, optimization of interventions, and study design in the larger trial. Finally, we will examine theoretical therapeutic mechanisms to explore the hypotheses that in MBI, mindfulness, monitoring/acceptance, and executive function will improve and in CBT, thoughts and pleasant activities will improve, compared to each other and to HealthEd.

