Decreasing insulin resistance is key to T2D prevention. T2D is preventable,^{14,15} and prevention focuses on decreasing insulin resistance, the major physiological antecedent to T2D.¹⁶ Insulin resistance refers to diminished sensitivity of the hormone insulin to uptake, utilize, and metabolize glucose by almost all of the body's tissues.¹⁷ It is well-established that progression of worsening insulin resistance triggers the onset of T2D.¹⁸ Therefore, development of effective interventions to decrease insulin resistance would significantly reduce T2D among at-risk youth.^{16,19-21} Because obesity, or high body weight (BMI ≥95th percentile for age and sex), is a contributor to insulin resistance,²² the standard-of-care for T2D prevention involves lifestyle intervention to decrease energy intake and increase physical activity, with the primary goal of weight loss.^{14,15,23} Although this approach has demonstrated efficacy for diminishing T2D risk in adults,^{14,15} lifestyle programs unfortunately show insufficient effectiveness in adolescents, particularly racial and ethnic minority and low-income youth.^{24,25} Despite some promising short-term effects, lifestyle programs are costly and intensive (e.g., 2-3 sessions per week for 6 months), making adherence a challenge and weight regain common following the program's termination.²⁶⁻²⁹

Adolescence is a sensitive period to intervene to potentially alter the long-term course of insulin resistance and T2D.¹⁸ Puberty is characterized by a natural rise in insulin resistance,^{30,31} and continued exacerbation of insulin resistance in adolescents at risk for T2D plays a key role in the trajectory toward T2D.¹⁸ Furthermore, adolescence is characterized by highly dynamic emotional, cognitive, and behavioral changes that affect insulin resistance,³⁰⁻³² offering a window of opportunity for psychological-physical integrative health interventions to decrease psychological distress, improve insulin resistance and, consequently, lessen T2D risk in at-risk

teenagers.

Depression in adolescence is common and a risk factor for insulin resistance/T2D.

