3.8 Randomization and Stratification

A separate randomization sequence will be created for each site. Within site, we will create four strata by crossing sex (male, female) and age (12-14 years, 15-17 years) and we will use permuted blocks within each stratum to ensure the three intervention conditions are balanced. A statistician in the Children's Hospital Colorado's Biostatistics Core, other than the study lead statistician [name], will create the computerized randomization sequence and enter the sequence into REDCap's randomization module. The randomization sequence will be created in randomly permuted blocks stratified by site, sex, and age. Permuted blocks will be restricted so that for each cohort of $n=15$, the conditions will be balanced. REDCap's randomization module conveniently conceals the randomization sequence. The lead research coordinator will be responsible for using the REDCap randomization module to carry out randomization of eligible participants.

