- i. Pubertal staging: As puberty is related to insulin resistance,¹⁸ Tanner staging for breast and pubic hair (females) and testicular volume and pubic hair (males) will be performed by a trained medical provider. To accommodate medical provider schedules and participant/family schedules, pubertal staging may be carried out at screening visit 1 instead. Additionally, Tanner stage will be collected through adolescents' self-report on a validated questionnaire.¹⁶² Participants will be asked to define their physical development based on illustrations of their external characteristics, which corresponded to Tanner stages 1-5 of breast and pubic hair development for girls and Tanner stages 1-5 of testicular volume and pubic hair development for boys.
- ii. Body composition: During a fasted state, fat/fat-free mass will be assessed via air displacement plethysmography (BodPod), which shows good test-retest reliability and convergence with dual energy x-ray absorptiometry,¹⁶³ but is far more cost-effective.
- iii. Stress-related behavior: Several measures of hedonic eating, referring to eating for reward/pleasure as opposed to physiological hunger,⁷⁵ will be collected. The overeating section of the Eating Disorder Examination (EDE), a semi-structured interview, will be administered by a trained research assistant to identify frequency of 3 types of eating episodes: objective binge (overeating with loss of control), subjective binge (loss of control without objective overeating as assessed by the interviewer, but viewed as excessive by the interviewee), and objective overeating (overeating without loss of control). Tests of the EDE's discriminant validity, internal consistency, concurrent validity and test-retest reliability support its use in adolescents.¹⁶⁴⁻¹⁶⁶ The EDE may be conducted in-person during the screening visit, or alternatively, may be conducted remotely using secure video software or by phone.

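### Baseline pubertal stage is collected for its link to insulin resistance but is not a planned covariate in the insulin-resistance models, at a small cost in precision

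*Combined protocol and SAP*

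**What the plan says.** Section 2.1 gives the biological premise: "Puberty is characterized by a natural rise in insulin resistance". Section 6.2.4 (Screening Visit 2) gives the reason for staging, "As puberty is related to insulin resistance", and the method: "Tanner staging for breast and pubic hair (females) and testicular volume and pubic hair (males) will be performed by a trained medical provider". A self-report questionnaire on stage is collected as well.

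Section 8.6.2 plans mixed models with group, time and their interaction, covering insulin resistance among other outcomes. The baseline value of the outcome is a firm covariate. On adiposity the text reads: "Models will be adjusted for baseline adiposity and change in adiposity". For anything further the team "will also consider adjustment for baseline age, sex, race/ethnicity, particularly if these variables are not balanced across study groups". Pubertal stage is not named anywhere in Section 8 as covariate, moderator or subgroup. The nearest text is open-ended: "We will also examine participant characteristics associated with these outcomes".

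Section 3.8 stratifies randomization within site by sex and by two age bands, 12-14 and 15-17 years.

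**The concern.** A variable collected for its relation to a biomarker has no stated place in that biomarker's analysis. Its closest proxy, age, is optional, and whether it enters may depend on imbalance seen in the data.

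The gap concerns change over time. Adolescents of the same age and sex can differ in stage, and they may change differently over the following year according to where they start. The 1-year visit may fall as late as 18 months after the first session (Section 6.2.6). A baseline HOMA-IR or ISI value says little about that future change.

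Section 8.6.2 makes a signal on insulin sensitivity one goal of the secondary analyses and wants the pilot to be as informative as possible. Leaving out a baseline predictor that is already in the database works slightly against that goal.

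**Working it through.** **The plan's own figure.** Section 8.6.2 says that the pilot, after attrition, is powered for a standardized effect of 0.3 with one-sided 80% intervals. It states neither the final n nor a power level, so the figure cannot be reproduced exactly. What can be computed is the distance from the estimate to the one-sided 80% limit, z(0.80) × √(2/n), with z(0.80) = 0.8416. Here n is the number per arm and the residual SD before adding stage is set to 1.

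- 28 per arm (70% retention of 40, Section 9.3.2): 0.225
- 32 per arm (4 clusters of 8, Section 8.2): 0.210
- 34 per arm (15% loss from 40, Section 8.2): 0.204

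These ignore clustering, which does not affect the relative comparison below.

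**What stage could add.** The documents do not say how much variance stage explains, so the following are assumptions:

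- Stage correlates r = 0.2 to 0.4 with insulin resistance, equally at baseline and follow-up.
- Baseline and follow-up insulin resistance correlate ρ = 0.4 to 0.7.
- Where age is also in the model, age and stage correlate 0.6, and age relates to insulin resistance only through stage (correlation 0.6r).

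Given the baseline outcome, the partial R² of stage is r²(1−ρ) / [(1−r²)(1+ρ)]. Adding stage multiplies the interval width by √(1−R²).

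- Smallest case, r = 0.2, ρ = 0.7: 0.04 × 0.3 / (0.96 × 1.7) = 0.0074; narrowing 1 − √0.9926 = 0.37%.
- Largest case, r = 0.4, ρ = 0.4: 0.16 × 0.6 / (0.84 × 1.4) = 0.0816; narrowing 1 − √0.9184 = 4.17%.

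| r | ρ | R² given baseline | narrowing | R² given baseline and age | narrowing |
|---|---|---|---|---|---|
| 0.2 | 0.7 | 0.0074 | 0.37% | 0.0048 | 0.24% |
| 0.2 | 0.4 | 0.0179 | 0.90% | 0.0117 | 0.59% |
| 0.3 | 0.5 | 0.0330 | 1.66% | 0.0221 | 1.11% |
| 0.4 | 0.7 | 0.0336 | 1.70% | 0.0231 | 1.16% |
| 0.4 | 0.4 | 0.0816 | 4.17% | 0.0569 | 2.89% |

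The range is about 0.4% to 4%, or 0.2% to 3% if age is in the model. With 32 per arm, the 0.210 becomes at best 0.2104 × 0.9583 = 0.202.

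**In power terms.** For a difference of 0.3 SD at one-sided 0.20 with 32 per arm, power is 64.0% now. It would be 66.4% at R² = 0.10, which is above the range in the table.

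**A larger gain.** If stage predicted later change strongly, its correlations with baseline and follow-up values would differ and R² could exceed the table. At R² = 0.20 the interval narrows by 1 − √0.80 = 11% and power reaches 69.2%. Nothing in the documents supports a value that high.

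**Chance imbalance is not a second cost.** Suppose 40% are below Tanner 5 (assumption), with 34 per arm and no stratification. The between-arm difference in that proportion then has SD √(2 × 0.4 × 0.6 / 34) = 0.119. With R² = 0.10, the stage effect is √(0.10 / 0.24) = 0.65 SD. The arm contrast therefore shifts by about 0.65 × 0.119 = 0.08 SD, against a standard error of √(2/34) = 0.24. In variance terms this is about 0.0059 / 0.0588 = 0.10, the same 10% already counted as R².

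**The case against.** The strongest case against the point is that the plan already handles most of it. Baseline HOMA-IR or ISI is a firm covariate, within-participant correlation is modelled, allocation is stratified by sex and age band, age and sex may be added, and participant characteristics will be explored. The affected analyses are secondary. Section 8.6.2 says that power for them may be insufficient and that lack of a signal need not stop the main trial. The primary outcomes, fidelity and recruitment, are untouched.

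Most of this stands, and it limits the point to a refinement. It does not close the gap:

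- Baseline adjustment removes stable differences between adolescents, not what stage predicts about later change.
- Stratification is a coarse proxy. Four sites by four strata give 16 cells, or 120/16 = 7.5 adolescents per cell and 2.5 per arm.
- The clause on participant characteristics neither names puberty nor puts it in the arm comparison.

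A further objection is that a stage main effect only shifts both follow-ups by the same amount, whereas the argument is about different change over the year. That is right, and it is why a stage-by-time term is needed.

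A reader might infer that all pubertal variation is left in the noise, or that the arm comparison is biased. The documents support neither reading. The planned adjustment and stratification take out much of the variation, and under randomization an omitted baseline covariate costs precision only. Nor do the documents say that puberty drives insulin resistance: they describe a relation and a natural rise.

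**Conclusion.** The point holds as a minor improvement to the analysis plan. Pubertal stage is collected for its relation to insulin resistance and is missing from the covariates for the insulin-resistance models, while its nearest proxy is discretionary. The expected loss is about 0.2% to 4% in interval width. That range rests on assumed correlations, including equal correlation of stage with insulin resistance at both visits. No stated figure and no primary conclusion changes.

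**What to change.** In Section 8.6.2, before database lock, prespecify baseline pubertal stage and a stage-by-time term as fixed terms in the HOMA-IR and ISI models, regardless of observed balance. State the source (provider-rated, self-report where the exam is missing) and the coding (below Tanner 5 versus 5). Section 3.9 keeps the principal investigator and statistician blinded until lock, so this can still be a genuine prespecification.

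Use baseline stage only. Later stage is measured after randomization and is not collected at 6 weeks. At 1 year, Section 6.2.6 lists Tanner staging without restriction, while Section 7.3 limits repeat staging to those below Tanner 5 at baseline. Those two passages should be reconciled.

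The cost is wording, with no new data. With binary stage, the baseline value as covariate and two follow-ups as outcomes, the main effect takes one degree of freedom and the interaction another. Where self-report replaces the exam, some measurement error is mixed in, so the number of such cases should be reported.
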